#### 4.3.4 Biopsy-Proven Acute Rejection (BPAR)

[figure not shown]
A rejection is considered a BPAR if:

- Primary clinical diagnosis = “Acute rejection” or “Acute and chronic rejection” from Kidney allograft rejection eCRF page; **AND**
- Acute T-Cell mediated rejection = “Yes” or Acute antibody mediated rejection = “Yes” from Kidney allograft biopsy eCRF page.

Date of BPAR will be “date rejection was first suspected” on the Kidney allograft rejection eCRF, or if missing, the first available date of the biopsy of the particular rejection episode on the Kidney allograft biopsy eCRF page (note: BPAR is a subset of AR).

The BPAR episode can be classified into rejection types: t-cell mediated, antibody mediated, or any combination of those (see an illustration in [Figure 4-2](#)).

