Control regimen	Drug regimen used post-randomization as a comparator to evaluate comparative effects of the investigational drug (i.e. the combination of MPA and a CNI- either tacrolimus or cyclosporine)		
Enrollment	Point/time of subject entry into the study; the point at which informed consent must be obtained (i.e. prior to starting any of the procedures described in the protocol)		
Extension	Study period from Month 12 visit to completion of Month 24 visit regardless of treatment status (i.e. can be on or off randomized regimen)		
Investigational regimen	The investigational drug regimen tested in the study post-randomization (i.e. the combination of everolimus and a CNI- either tacrolimus or cyclosporine)		
Lost to follow-up	Those subjects whose status is unclear because they fail to appear for study visits without stating an intention to withdraw and cannot be contacted		
Subject Number	A number assigned to each subject who enrolls into the study		
Period	A distinct stage in the subjects' participation in the study, each period serves a purpose in the study as a whole		
Premature subject withdrawal	Point when the subject exits from the study prior to the planned completi of all assessments, synonymous with study discontinuation, not the sam as treatment discontinuation		
Primary Treatment Period	Study period from randomization to completion of Month 12 visit, regardless of treatment status (i.e. can be on or off randomized regimen)		
Screening period	Period from signing informed consent to successful completion of the transplant procedure		
Study Completion	Point at which the subject came in for a final evaluation visit at Month 24 or complete discontinuation from the study if prior to Month 24		
Study drug/ treatment	Any single drug or drug regimen administered to the subject as part of the required study procedures in any study period, includes everolimus, tacrolimus, cyclosporine, basiliximab, MPA and corticosteroids		
Treated biopsy proved acute rejection (tBPAR)	An acute rejection episode documented by histological evidence for which anti-rejection therapy (e.g. steroids, antibody or increase in study regimen immunosuppression) was given.		
Treatment discontinuation	Point when subject permanently stops taking study/investigational or control treatment drug/regimen for any reason, not the same as study discontinuation/premature subject withdrawal		

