6.4 Efficacy

Treated Biopsy Proven Acute Rejection (tBPAR)

A treated BPAR is any condition where the subject received anti-rejection treatment and was histologically diagnosed as acute rejection (according to the Banff 2009 criteria, Appendix 6). Renal biopsies will be collected for all cases of suspected acute rejection.

Kidney allograft biopsy

For all suspected rejection episodes, regardless of initiation of anti-rejection treatment, an allograft biopsy must be performed within 48 hrs. Biopsies will be read by the local pathologist according to the updated Banff 2009 criteria (Appendix 6). The results of the biopsy read by the local pathologist will be listed on the Kidney Allograft Biopsy CRF. The results will be used for subject management for acute rejection. The local pathologist will remain blinded to

treatment. Any biopsies performed according to local practice (e.g. not for cause) should also be recorded.

Graft Loss

The allograft will be presumed to be lost on the day the subject starts dialysis and is not able to subsequently be removed from dialysis. If the subject undergoes allograft nephrectomy prior to starting permanent dialysis, then the day of nephrectomy is the day of graft loss. The reason for graft loss will be recorded on the Graft Loss CRF. This will be reported on the M12 or M24 study completion CRF with Graft Loss as the reason for study discontinuation and on the appropriate Dosage Administration Record CRF(s) if death occurs while on randomized treatment. Graft loss is considered a Serious Adverse Event and should be reported on the Adverse Event CRF (as serious) and the SAE reported to the local Novartis Drug Safety and Epidemiology Department local Novartis Drug Safety and Epidemiology (DS&E) Department within 24 hr.

Death

In the event of subject death, the SAE leading to Death should be reported to Novartis DS&E within 24 hr. The events leading to the death should be entered on the Adverse Event CRF and the death should be indicated on the appropriate Dosage Administration Record CRF(s) (if death occurs while on randomized treatment) and on the Study Completion CRF.

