### 2.3.2 Patient Demographics and Baseline Characteristics

Demographic and background information will be summarized based on the FAS population.

Incidence rates of diabetes at baseline (see the definition in [Section 2.8.3.3](#)) and delayed graft function will be also summarized.

Delayed graft function is defined when any of the following criteria are met within 21 days (end day of Week 2 visit window) after transplant:

- AE eCRF page: MedDRA lower level term includes words: “graft dysfunction” or “graft function delayed”; verbatim contains “delayed graft function” or “DGF”.
- Kidney Allograft Rejection eCRF page: “Primary reason rejection was suspected” = Delayed or slow recovery of graft function post-revascularization” or “Primary clinical diagnosis” = “delayed graft function”.

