### 4.3 Definition/Derivation of Efficacy Variables

All efficacy endpoints regarding biopsy described below will be identified from local pathologists' evaluation of all biopsy readings. All acute rejections are recorded in the clinical database on the Kidney allograft rejection and Kidney allograft biopsy eCRFs.

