#### 4.3.2 Acute Rejection (AR)

A rejection is considered an AR if:

- Primary clinical diagnosis = “Acute rejection” or “Acute and chronic rejection” from Kidney allograft rejection eCRF page; **OR**
- Antibody-mediated rejection (see above); **OR**
- Acute T-Cell mediated rejection = “Yes” from Kidney allograft biopsy eCRF page.

Date of AR will be “date rejection was first suspected” on the Kidney allograft rejection eCRF, or if missing, the first available date of the biopsy of the particular rejection episode on the Kidney allograft biopsy eCRF page.

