#### 4.3.3 Treated Acute Rejection (tAR)

A rejection is considered a tAR if:

- Acute rejection (see above); **AND**
- Was anti-rejection therapy administered? = “yes” from Kidney allograft rejection eCRF

Date of tAR will be the date of the corresponding AR (note: tAR is a subset of AR).

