**Figure 4-2 Example of a rejection episode**

#### **4.3.5 Treated Biopsy-Proven Acute Rejection (tBPAR)**

A rejection is considered a tBPAR if:

- Biopsy-proven acute rejection (BPAR) (see above) *and*
- Was anti-rejection therapy administered? = “yes” from Kidney allograft rejection eCRF page

Date of tBPAR will be the date of the corresponding BPAR (note: tBPAR is a subset of BPAR, and it is also a subset of tAR).

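### The SAP defines tBPAR more narrowly than the protocol, by adding a site clinical-diagnosis condition to the primary and key secondary endpoints

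*SAP*

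**What the plan says.** **Protocol.** Section 6.4 reads: "A treated BPAR is any condition where the subject received anti-rejection treatment and was histologically diagnosed as acute rejection", with histology graded by Banff 2009 (Appendix 6). The glossary entry for tBPAR is worded slightly differently, "An acute rejection episode documented by histological evidence for which anti-rejection therapy" was given, and it also names no clinical-diagnosis field.

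**SAP.** Section 4.3.4 requires two things for BPAR. The first is "Primary clinical diagnosis = “Acute rejection” or “Acute and chronic rejection” from Kidney allograft rejection eCRF page; AND". The second is acute T-cell mediated or acute antibody mediated rejection marked Yes on the biopsy eCRF. Section 4.3.5 defines tBPAR as a BPAR for which anti-rejection therapy was recorded, so it inherits both conditions.

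Sections 4.3.2 and 4.3.3 work differently. AR joins its conditions by OR, so "Acute T-Cell mediated rejection = “Yes” from Kidney allograft biopsy eCRF page" is enough by itself, and tAR adds only "Was anti-rejection therapy administered? = “yes” from Kidney allograft rejection eCRF".

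The lead-in to section 4.3 says: "All efficacy endpoints regarding biopsy described below will be identified from local pathologists' evaluation of all biopsy readings". Its next sentence says that acute rejections are recorded on both the rejection and the biopsy eCRFs.

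Section 2.3.2 shows that the primary clinical diagnosis field can hold other values: its definition of delayed graft function uses that entry on the same rejection page.

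**The concern.** The SAP condition can only remove events. An episode that is biopsy positive and treated, but carries another primary clinical diagnosis, is tBPAR under protocol 6.4. Under the SAP it is AR and tAR, but neither BPAR nor tBPAR.

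tBPAR is a component of the primary endpoint (tBPAR or eGFR < 50 at Month 12) and of the key secondary endpoint (tBPAR, graft loss or death at Month 12). All three steps of the testing hierarchy therefore depend on the rule: the two non-inferiority tests and the superiority test.

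The trial is open label, while protocol 6.4 keeps the local pathologist blinded. The documents do not say who completes the clinical-diagnosis field. If site staff do, the extra condition places a judgement made with knowledge of the arm on top of a blinded reading. Unequal loss between arms is then possible, although nothing in the documents shows that it happens.

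**Working it through.** **1. The two definitions compared.** Each episode is classified by site diagnosis of acute rejection, positive biopsy, and treatment. Episodes that are untreated, or that have neither condition met, are not tBPAR under either document. The treated combinations are:

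| Site diagnosis | Biopsy positive | Treated | Protocol tBPAR | SAP tAR | SAP tBPAR |
|---|---|---|---|---|---|
| No | No | Yes | No | No | No |
| No | Yes | Yes | **Yes** | Yes | **No** |
| Yes | No | Yes | No | Yes | No |
| Yes | Yes | Yes | Yes | Yes | Yes |

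Of the eight combinations, exactly one differs, and none differs in the other direction. SAP tBPAR is thus a strict subset of protocol tBPAR. If the site-diagnosis condition is removed, the two agree in all eight.

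**2. When a dropped episode matters.** It changes a patient's primary status only if the patient has no other tBPAR and Month 12 eGFR is at least 50. It changes key secondary status only if there is no other tBPAR, graft loss or death. Below, a lost event means a patient with no other qualifying event.

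**3. Inputs.** From the documents: 1020 per arm, one-sided 0.025, a margin of 10 points for both non-inferiority tests, and a 50% primary event rate (protocol 9.4.2 and 9.7). Assumed: the number and arm of lost events, and the key secondary rates, for which the documents give no figure. Simple proportions stand in for Kaplan-Meier rates with little censoring.

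Probability of rejecting the null = Φ((margin − d)/SE − 1.96), where d is the difference in rates as the SAP would code them and SE = √[(p₁(1−p₁) + p₂(1−p₂))/1020] at those rates.

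**4. Check against the plan.** At 50% vs 50%, this gives non-inferiority power of 99.5% for N=1020 and 98.1% for N=816. Protocol Table 9-1 states >99 and 98, so the formula reproduces it.

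**5. Key secondary at the margin (assumed 22% vs 12%).** One lost event moves an arm by 1/1020 = 0.098 point. With no loss, SE = √[(0.22×0.78 + 0.12×0.88)/1020] = 0.01649 and the error is 2.5%. With 5 lost in everolimus (EVR), d = 0.10 − 5/1020 = 0.0951, SE = 0.0164, and Φ(0.0049/0.0164 − 1.96) = 4.8%.

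| Lost events | One-sided error, 22% vs 12% | Range, control rate 8% to 20% |
|---|---|---|
| 5 in EVR only | 4.8% | 5.2% to 4.4% |
| 10 in EVR only | 8.7% | 9.9% to 7.5% |
| 5 in MPA only | 1.2% | 1.1% to 1.3% |
| 10 in MPA only | 0.5% | 0.4% to 0.7% |
| 5 or 10 in each arm | 2.5% | 2.5% |
| 6 in EVR, 4 in MPA | 3.3% | 3.4% to 3.2% |

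**6. Primary endpoint and superiority.** Assume 10 discordant episodes in one arm, of which 25% to 50% have no other qualifying event, so 2.5 to 5 events are lost.

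| Test and true rates | Lost in EVR | Lost in MPA |
|---|---|---|
| Primary non-inferiority, 60% vs 50% | 3.2% to 4.1% | 1.9% to 1.4% |
| Superiority, 50% vs 50% | 3.2% to 4.1% | 1.9% to 1.5% |

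Power is hardly affected. At 50% vs 50%, with 10 events lost in MPA only, primary non-inferiority power falls from 99.5% to 98.3%.

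**The case against.** The best defence is that a clinical episode, confirmed by histology and then treated, is a reasonable operational reading of the protocol. The glossary starts from an acute rejection episode. Section 6.4 ties biopsy to suspected rejection and refers to Appendix 6, whose Banff note integrates clinical data as a second step. This softens the conflict without removing it: none of these passages names the eCRF field or requires a particular site diagnosis, and the section 6.4 definition names only treatment and histology.

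Two supporting points are weaker than they first look, and the objection to them stands. The SAP 4.3 lead-in goes on to name both eCRFs, so it may only be saying whose biopsy reading counts. The SAP document history logs changes between SAP versions, so its silence does not show an undisclosed departure from the protocol. It remains true that no justification appears anywhere.

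It is also fair that discordance is possible but not shown to occur. The diagnosis and the treatment item sit on the same form, and data checks and source verification could make disagreement rare. The larger error figures need all the loss to fall in one arm with the true difference exactly at the margin.

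Finally, AR, tAR, BPAR and tBPAR are all compared by arm (SAP 2.7.2.2), and protocol tBPAR lies between SAP tBPAR and tAR. The gap between those two is therefore an upper bound on discordance. It is only a bound, because tAR also includes rejections without biopsy proof, and no composite is planned on it.

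**Conclusion.** The concern holds. As written, the SAP excludes from tBPAR some episodes that the protocol's endpoint includes, in both composites and all three confirmatory tests, without stated reason. This should be fixed.

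The size is unknown. The error figures rest on assumed losses, assumed key secondary rates and true differences at the null boundary. They can go either way and vanish when losses are balanced. What is established is that the confirmatory results are sensitive to an unexplained rule, not that they are biased. Confidence is medium because the eCRF completion rules and SAP Figure 4-2 could not be seen.

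**What to change.** - In SAP 4.3.4, define BPAR as acute T-cell mediated or acute antibody mediated rejection marked Yes on the biopsy eCRF. In 4.3.5, define tBPAR as that plus anti-rejection therapy recorded as yes. Use this in the confirmatory analyses.
- Run the narrower rule as a sensitivity analysis of the primary and key secondary endpoints.
- Tabulate by arm the episodes that are biopsy positive and treated but carry another clinical diagnosis. If there are none, the table settles the matter.
- If the narrower rule was intended, state and justify it as a change from the protocol, and run the protocol definition as the sensitivity analysis.

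The cost is one derivation change, one sensitivity run and one table, all from fields already collected. The drawback is that some treated episodes that the site attributed mainly to another cause will count. These include findings on biopsies not done for cause, which protocol 6.4 also records, so tBPAR may vary more with centre biopsy practice.

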**Figure 4-2 Example of a rejection episode**

#### **4.3.5 Treated Biopsy-Proven Acute Rejection (tBPAR)**

A rejection is considered a tBPAR if:

- Biopsy-proven acute rejection (BPAR) (see above) *and*
- Was anti-rejection therapy administered? = “yes” from Kidney allograft rejection eCRF page

Date of tBPAR will be the date of the corresponding BPAR (note: tBPAR is a subset of BPAR, and it is also a subset of tAR).

#### **4.3.6 Antibody Treated Biopsy-Proven Acute Rejection**

A rejection is considered an antibody treated BPAR if:

- Biopsy-proven acute rejection (BPAR) (see above) *and*
- Was antibody treatment administered? = “yes” from Kidney allograft rejection eCRF page

Date of antibody treated BPAR will be the date of the corresponding BPAR (note: antibody treated is a subset of BPAR)

#### **4.3.7 Death**

Death will be recorded at Death eCRF. The date of event will be recorded at this *eCRF* as well.

#### **4.3.8 Graft Loss**

Graft loss will be recorded at Graft Loss eCRF. The date of graft loss will be recorded at this *eCRF* as well.

#### **4.3.9 Loss to Follow-Up**

Patients lost to follow-up for the composite efficacy failure (tBPAR, graft loss or death) for the 12-month analysis are defined as those who meet the following two conditions:

- Last contact day is < Day 316 (start day of the Month 12 visit window);
- Did not experience any efficacy event (of tBPAR, graft loss or death) up to the last contact day for the 12-month analysis.

Patients lost to follow-up for the composite efficacy failure (tBPAR, graft loss or death) for the 24-month analysis are defined as those who meet the following two conditions:

- Last contact day is < Day 631 (start day of the Month 24 visit window);
- Did not experience any efficacy event (of tBPAR, graft loss or death) up to the last contact day for the 24-month analysis

The date of lost to follow-up is the date of last study contact for the respective analysis (12 or 24-month analysis).

### 4.3.10 Composite Efficacy Failure

Several composite endpoints are defined as primary or secondary efficacy variables. The date of efficacy failure is calculated as the earliest available date among the individual components of the composite endpoint.

For the composite endpoints and each individual endpoint, if the date of the event is not available, then the event will be included in listings and the simple proportion efficacy tables, but excluded from survival analysis.

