5.5.12 Early study termination

The study can be terminated at any time for any reason by Novartis. Should this be necessary, the subject should be seen as soon as possible and treated as for a prematurely withdrawn subject. The investigator may be informed of additional procedures to be followed in order to ensure that adequate consideration is given to the protection of the subject's interests. The investigator will be responsible for informing IRBs and/or ECs of the early termination of the trial.

6 Visit schedule and assessments

Table 6-1 lists all of the assessments and indicates with an "X" when the visits are to be performed. "A" indicates assessments only to be performed for subjects maintaining the study regimen (i.e. EVR+CNI or MPA+CNI). Subjects should be seen for all visits on the designated day or as close to it as possible.

The day of randomization will be considered to be study Day 1. Subjects will make scheduled study visits on Day 4, at the end of Weeks 1, 2 and 4 at the end of Months 2, 4, 6, 9, 12, 18 and 24. All randomized subjects are expected to continue in the study up to Month 24 regardless of being on or off randomized treatment status. Subjects who discontinue their randomized study treatment regimen should be treated according to standard of care immunosuppression and return for the assessments indicated by X in Table 6-1. If they refuse to return for these assessments or are unable to do so, every effort should be made to contact them or a knowledgeable informant by telephone to determine the subject and graft status.

At a minimum, subjects will be contacted for safety evaluations (SAEs) during the 30 days following the last study visit. Documentation of attempts to contact the subject should be recorded in the source documentation.

Assessment schedule- Study Treatment to Month 24 Table 6-1

Study Period	Screening ¹		Treatment to Month 12									Extension Treatment to Month 24		
Visit	SCR	BL ²	D4	W1	W2	W4	M2	M4	М6	М9	M12	M18	M2 4	
Visit Number	1	99	101	102	103	104	105	106	107	108	199	201	299	
Informed Consent ¹	Х													
Demographics	Х													
Inclusion/	X	Х												
Exclusion														
Medical History	Х												 	
Kidney Transplant Background Recipient/Donor		X												
Kidney Transplant Procedure		Х												
Viral serology ³ Recipient/Donor		Х												
Pregnancy test ⁴	Х								Х		Х	Х	Х	
IRT call	S	S												
Screening Disposition ¹		Х												

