#### Testing strategy to control type I error:

Event rates will be compared between groups using the following hierarchical testing strategy:

- a. Non-inferiority of EVR+rCNI vs. MPA+sCNI will be evaluated based on the primary endpoint of tBPAR or eGFR (MDRD4)  $< 50 \text{ mL/min/1.73m}^2$  at Month 12 using a 10% non-inferiority margin (see [Section 2.5.2.1](#)).
- b. Non-inferiority of EVR+rCNI vs. MPA+sCNI will be evaluated with a 10% non-inferiority margin for the key secondary endpoint of tBPAR, graft loss or death at Month 12 (see [Section 2.6.2](#)).
- c. Superiority of EVR+rCNI to MPA+sCNI will be evaluated based on the primary endpoint of tBPAR or eGFR (MDRD4)  $< 50 \text{ mL/min/1.73m}^2$  at Month 12 (see [Section 2.5.2.2](#)).

The above hierarchical fixed hypothesis testing procedure will not inflate overall Type I error rate. Therefore, each hypothesis will be tested at the one-sided 0.025 significance level and no multiplicity adjustment is needed. For these statistical tests, one-sided p-values will be presented in the analysis outputs.

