**The alternative hypothesis:**

$H_{A2}$ :  $REVR_{+CNI} - R_{MPA+sCNI} < 0.10$  (non-inferiority margin): the difference in Kaplan-Meier event rate of the composite efficacy failure of tBPAR, graft loss or death at 12 months between the everolimus plus reduced CNI ( $REVR_{+CNI}$ ) and the MPA plus standard CNI arm ( $R_{MPA+sCNI}$ ) is less than 10%.

For this analysis, the event rate of the composite efficacy failure of tBPAR, graft loss or death will be estimated with Kaplan-Meier product-limit formula. Greenwood's formula will be used to estimate variance of failure rates and to derive Z-test based confidence interval for the difference in failure rate between the everolimus plus reduced CNI and the MPA plus standard CNI arm.

A Kaplan-Meier table and plot will be produced. The differences between the two KM curves, corresponding to the two treatment arms, will be tested pair-wise using the log-rank test. In

these analyses, patients with event-free will be censored with the censoring time as defined as the Last Contact Day.

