#### 4.2.4 Imputation of Incomplete Dates

Although not the rule, partially or completely missing dates occur. Known dates with this issue are the start date on the Medical History eCRF page, start and end dates on the Concomitant Medications eCRF page or Surgical and Medical Procedures eCRF page, and occasionally, start and end dates on the Adverse Event eCRF.

Any date incompletely reported is split into its day, month, and year components. In SAS, a numeric date variable can only be defined if all three date components are known; incomplete dates are to be handled as text strings (character-type variables); as such, they could not be easily processed. An imputation rule for incomplete dates will be performed.

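### Known failures with no available date are left out of the Kaplan-Meier key secondary non-inferiority test (mainly deaths and graft losses)

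*SAP*

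**What the plan says.** The rule is in SAP 4.3.10 and covers composites and single endpoints alike. Where no event date is on record, the SAP's instruction reads: "then the event will be included in listings and the simple proportion efficacy tables, but excluded from survival analysis". The same section limits its reach for composites: "The date of efficacy failure is calculated as the earliest available date among the individual components of the composite endpoint".

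The key secondary test is a survival analysis. Under SAP 2.6.2 the 12-month failure rate "will be estimated with Kaplan-Meier product-limit formula", and "Greenwood's formula will be used to estimate variance of failure rates" and to build the confidence interval for the difference. In the testing strategy of SAP 2.5.2 this is step (b): non-inferiority "will be evaluated with a 10% non-inferiority margin for the key secondary endpoint of tBPAR, graft loss or death at Month 12". Step (c), superiority on the primary endpoint, is reached only if (b) succeeds.

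Event dates come from these places:

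- **Rejection (SAP 4.3.4, 4.3.5).** The date rejection was first suspected or, if missing, the first biopsy date of the episode. tBPAR inherits this date.
- **Death and graft loss (SAP 4.3.7, 4.3.8).** Each has its own eCRF, and the SAP gives no fallback.
- **Incomplete dates (SAP 4.2.4).** The imputation matrices cover adverse event start dates and concomitant medication start and end dates. No rule covers efficacy events.

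The SAP does not say whether a patient whose only event is undated leaves the Kaplan-Meier analysis or stays in it as censored, or on what day. The censoring rules in SAP 2.6.2 and 2.6.3 concern patients who are event-free or lack an evaluation. This patient is neither.

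**The concern.** A failure that the database records as having happened is treated as a non-failure in a confirmatory test. If the patient is censored at the last contact day, which SAP 2.1.1.3 takes from the latest date in the database, the patient may also count as event-free time after the failure.

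The margin is an absolute difference. When the everolimus rate is truly higher, removing the same proportion of events from both arms removes more events from everolimus and pulls the difference towards zero, which favours non-inferiority. At stake are the error rate of step (b) and access to step (c). The SAP specifies no simple-proportion non-inferiority test of this endpoint at Month 12 as a check; only the futility calculation (SAP 2.12.3.3) uses the raw rate.

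Protocol section 6 provides one route by which imprecise dates could arise. For patients who will not or cannot return, "every effort should be made to contact them or a knowledgeable informant by telephone to determine the subject and graft status".

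**Working it through.** **Inputs from the documents.** N = 1020 per arm (SAP 3), margin 10 points and one-sided 0.025 (SAP 2.5.2).

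**Assumptions, not in the documents.** Key secondary control rate of 10%, 15% or 20%; number or share of undated events.

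**Step 1: the plan's own figures.** No power is stated for the key secondary test. For the primary endpoint at 50% in each arm, Protocol Table 9-1 gives non-inferiority power of >99, 98, 97, 95 and 92% for N = 1020, 816, 714, 653 and 571. With power = Φ(0.10/SE − 1.96) and SE = √(2 × 0.25/N), the results are 0.9947, 0.9812, 0.9655, 0.9509 and 0.9221. The table is reproduced, and the undated-event rule does not make any of it wrong.

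**Step 2: effect of one event.** 1/1020 = 0.098 point if the patient stays in the risk set as event-free. Five events in one arm: 5/1020 = 0.49 point.

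**Step 3: type I error at a true difference of 10 points, equal share f undated in both arms.** With control 15% and everolimus 25%, the expected events are 153 and 255. If undated patients are treated as event-free, each rate becomes p(1 − f). If they are dropped, it becomes p(1 − f)/(1 − pf). The probability of declaring non-inferiority is Φ((0.10 − difference)/SE − 1.96), with unpooled SE.

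- f = 1% (about 1.5 and 2.6 events), event-free: rates 0.1485 and 0.2475, difference 0.099, SE = √[(0.1485 × 0.8515 + 0.2475 × 0.7525)/1020] = 0.01751, z = 0.001/0.01751 − 1.96 = −1.903, giving 0.0285.
- f = 5% (about 7.7 and 12.8 events), event-free: rates 0.1425 and 0.2375, difference 0.095, SE = 0.01724, z = 0.005/0.01724 − 1.96 = −1.670, giving 0.0475.

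| Share undated | Event-free, control 15% (range over 10% and 20%) | Dropped, control 15% (range over 10% and 20%) |
|---|---|---|
| 0 | 0.025 | 0.025 |
| 1% | 0.0285 (0.0290 to 0.0282) | 0.0271 (0.0277 to 0.0266) |
| 2% | 0.0325 (0.0335 to 0.0319) | 0.0293 (0.0308 to 0.0283) |
| 5% | 0.0475 (0.0511 to 0.0452) | 0.0373 (0.0419 to 0.0342) |

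If undated events are counted as failures, the error stays at 0.025.

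**Step 4: how near the margin the result must be.** With 153 control events (15%), non-inferiority first fails at 221 everolimus events (difference 6.67 points, upper limit 10.01%). That is 221 − 153 = 68 more than control; the figure is 72 at a 10% control rate and 65 at 20%. With five undated everolimus events kept as event-free to Month 12, the conclusion flips only if the full everolimus count lies between 221 and 225.

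**Step 5: Kaplan-Meier and Greenwood check on constructed data, 153 against 226 events.**

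- Five undated in everolimus only: upper limit 10.52% when counted; 10.07% if censored at the event time, 10.01% if censored at the end, 10.13% if dropped.
- Five undated in each arm: 10.48% to 10.53% under the rule, against 10.52% when counted. Equal counts nearly cancel. The bias in step 3 comes from equal shares, which mean more lost events in the arm with more events.

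**The case against.** The strongest case is that this gap will rarely matter. Death and graft loss have dedicated eCRFs that record the date, and both go through SAE reporting within 24 hours (Protocol 6.4, 7.2), with full source verification of SAE documentation (Protocol 8.1). Protocol 6.4 already defines the day of graft loss by permanent dialysis or nephrectomy. The list in SAP 4.2.4 that opens "Known dates with this issue are the start date on the Medical History eCRF page" does not include the death, graft loss or rejection pages. Undated events remain in listings and simple-proportion tables, and the wider composite that adds eGFR below 50 is analysed as a proportion (SAP 2.7.2.1). All of this stands: few undated events should be expected. It does not change what the rule does to those that occur, and the proportion analyses are not the gatekeeping test.

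Three stronger readings are tempting, but the documents do not support them.

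- *Every partial date is lost.* SAP 4.3.10 refers to a date that is not available, not to an incomplete one. Loss of partial dates is an inference from SAP 4.2.4, which says a numeric SAS date needs day, month and year and offers imputation only for adverse events and concomitant medication.
- *tBPAR is exposed as much as death.* It is lost only if both the suspicion date and the biopsy date are missing, and a biopsy is part of its definition. In the composite, any other dated component rescues the patient.
- *The loss falls mainly on everolimus.* Nothing shows that one arm has more remote follow-up or more undated events. The argument does not need it.

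A further fair point concerns the remedy. The endpoint is failure by Month 12, with a per-patient cut-off (SAP 2.1), and an event with no date cannot always be placed before that cut-off. The replacement text has to cover this case.

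**Conclusion.** The concern holds in this limited form. A stated rule turns known failures into non-failures in the only non-inferiority analysis of the key secondary endpoint in the FAS, and the bias favours non-inferiority when equal shares are undated and the everolimus rate is truly higher. The practical exposure is a death or graft loss with no usable date and no other dated component.

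The error rates in the table depend on assumed control rates, assumed missingness and a true difference exactly at the margin. They show sensitivity and are not a forecast. A reader might infer that the trial's error control has failed; the documents give no count of undated events and so cannot show that. At equal assumed rates of 10% to 20%, power for this test exceeds 99.9%, so a handful of undated events would matter only close to the boundary. The sentence is still worth replacing, because the change is cheap and the test is confirmatory.

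**What to change.** Replace the last sentence of SAP 4.3.10 with a rule along these lines:

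1. An event known to have occurred by the Month 12 cut-off counts as an event in the Kaplan-Meier analysis.
2. If its date is missing, take the earliest documented evidence: biopsy, start of anti-rejection therapy, dialysis log, nephrectomy or SAE record.
3. If there is none, impute a date between the last contact known to be event-free and the first record of the event, bounded by any known month or year.
4. If the event cannot be placed before or after the cut-off, count it as an event by the cut-off in the main analysis, and censor it at the last contact known to be event-free in a sensitivity analysis.
5. List the imputed dates and report their number by arm.

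The same text would serve the other Kaplan-Meier endpoints, with the corresponding Month 24 limit. The cost is one paragraph and a small derivation, and the failure rate may come out slightly less favourable. If no event is undated, no result changes.
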